6.5. Dose Modification

The study design does not allow for dose modifications.

6.6. Continued Access to Study Intervention after the End of the Study

Participants will not receive any additional treatment from GSK after they discontinue or complete the study (i.e., after the Follow-up Visit). Participants experiencing signs and symptoms suggestive of infection recurrence or relapse at the Follow-up Visit will be assessed and treated per the investigator's judgement.

6.7. Treatment of Overdose

For this study, any dose of Gepotidacin or Nitrofurantoin greater than 3000 mg or 200 mg within a 24-hour time period, respectively, will be considered an overdose, as further detailed in the SRM.

There is no specific antidote for overdose with a bacterial topoisomerase inhibitor. In the event of a suspected overdose, it is recommended that the appropriate supportive clinical care should be instituted, as dictated by the participant's clinical status.

Occasional incidents of acute overdosage of nitrofurantoin have not resulted in any specific symptoms other than vomiting (refer to the package insert). Induction of emesis is recommended. There is no specific antidote, but a high fluid intake should be maintained to promote urinary excretion of the drug.

In the event of an overdose, the investigator should:

1. Contact the medical monitor immediately.
2. Closely monitor the participant for AEs/SAEs and laboratory abnormalities until study intervention can no longer be detected systemically (at least 72 hours).
3. Obtain a plasma sample for PK analysis within 24 hours from the date of the last dose of study intervention if requested by the medical monitor (determined on a case-by-case basis).
4. Document the quantity of the excess dose as well as the duration of the overdosing in the CRF.

Decisions regarding dose interruptions will be made by the investigator in consultation with the Medical Monitor based on the clinical evaluation of the participant.

6.8. Concomitant Therapy

Any medication or vaccine (including over-the-counter or prescription medicines, vitamins, and/or herbal supplements) that the participant is receiving within 30 days prior to the Baseline Visit or receives during the study must be recorded in the eCRF. In addition, any antimicrobial use within 6 months prior to the Baseline Visit or during the study must be recorded in the eCRF. The concomitant therapy name must be recorded in the eCRF along with the following:

- reason for use
- dates of administration including start and end dates
- dosage information including dose and frequency

The medical monitor should be contacted if there are any questions regarding concomitant or prior therapy.

6.8.1. Permitted Medications and Nondrug Therapies

The use of H₁ antihistamines not associated with QT prolongation is allowed (e.g., loratadine, cetirizine, ebastine, and fexofenadine). The use of topical, nonsystemic antibacterials (e.g., topical clindamycin, fradiomycin or polymyxin) and topical, nonsystemic antifungals (e.g., topical clotrimazole, tolnaftate, or ketoconazole) is allowed throughout the study.

Acetaminophen use is permitted throughout the study as it does not mask symptoms of the disease under study. Low-dose aspirin (≤ 100 mg/day) is permitted for the prevention of cardiovascular (CV) disease events.

6.8.2. Prohibited Medications and Nondrug Therapies

At the time of enrollment and/or during the study from the Baseline Visit through the Follow-up Visit, the participant is prohibited from use of the following medications.

- Treatment with other systemic antimicrobials (e.g., oral ciprofloxacin, amoxicillin/clavulanate, cephalaxin, or doxycycline) within 1 week before study entry, unless other systemic antimicrobials are needed as additional therapy for the infection under study (acute uncomplicated cystitis), including recurrence of the infection or new infection.

At the time of enrollment and/or during the study from the Baseline Visit through the TOC Visit, the participant is prohibited from use of the following medications and nondrug therapies:

- An investigational product within 30 days or 5 half-lives, whichever is longer, of the Baseline Visit.
- Treatment with systemic antifungals (e.g., oral fluconazole, itraconazole, or terbinafine) within 1 week before study entry.
- Immunosuppressive therapy, including corticosteroid therapy (>40 mg/day prednisolone or equivalent for >1 week, ≥ 20 mg/day prednisolone or equivalent for >2 weeks, or prednisolone or equivalent ≥ 10 mg/day for >6 weeks).
- QT-prolonging drugs or drugs with known TdP risk, per the www.crediblemeds.org “Known Risk of TdP” category, at the time of their Baseline Visit, which cannot be safely discontinued from the Baseline Visit to the TOC Visit. Details regarding website access are provided in the SRM. Of note, ondansetron is not allowed from the Baseline Visit to the TOC Visit due to its known TdP risk.

Note: Crediblemeds.org categorizes drugs into 4 categories. The only category for exclusion in this study is the “Known Risk of TdP” category; participants taking drugs that meet criteria of other categories are NOT excluded from participation.

- Strong CYP3A4 inhibitors.
- St John’s wort or other strong CYP3A4 inducers are not permitted from 14 days before study entry through the TOC Visit.

- Prescription, nonprescription, or supplements that may impact UTI clinical or microbiological efficacy outcomes including, but not limited to, *Uva ursi*, D-mannose, cranberry tablets, nonsteroidal anti-inflammatory drugs including ibuprofen and cyclooxygenase-2 inhibitors, and uricosuric drugs (e.g., probenecid). Aspirin (doses >100 mg/day) is not permitted.

In addition, antacid preparations containing magnesium trisilicate are prohibited from the start of study treatment at the Baseline Visit throughout the completion of the dosing period (i.e., until all 10 doses of study treatment have been received).

Due to the gepotidacin's property of acetylcholinesterase inhibition, the concomitant use of succinylcholine or nondepolarizing paralytic agents is also prohibited. Caution should be used in participants who have a condition requiring medication that may exacerbate the inhibition of acetylcholinesterase, or neuromuscular blocking agents.

7. DISCONTINUATION OF STUDY INTERVENTION AND PARTICIPANT DISCONTINUATION/WITHDRAWAL

Discontinuation of specific sites or of the study as a whole are detailed in Section 10.1.

7.1. Discontinuation of Study Intervention

In rare instances, it may be necessary for a participant to permanently discontinue study intervention. If study intervention is permanently discontinued, the participant will remain in the study to be evaluated for safety and efficacy. See the SoA (Section 1.3) for data to be collected at the time of discontinuation of study intervention and follow-up and for any further evaluations that need to be completed.

Participants may voluntarily discontinue study treatment at any time. The investigator may also, at his or her discretion, discontinue the participant from study treatment at any time and initiate appropriate alternative therapy.

Reasons for study treatment discontinuation may include the following:

- Adverse event
- Protocol deviation
- Termination of the study by GSK
- Investigator discretion
- Lack of efficacy

Note: Pathogen identification or in vitro resistance of recovered uropathogens is not a reason for study treatment discontinuation.

The reason for study treatment discontinuation will be recorded in the eCRF. Participants who discontinue study treatment for the reasons above will not be considered withdrawn from the study and should attend all subsequent study visits (see Section 1.3).

[figure not shown]
7.1.1. Liver Chemistry Stopping Criteria

Liver chemistry stopping, and increased monitoring criteria have been designed to assure participant safety and evaluate liver event etiology.

Discontinuation of study intervention for abnormal liver tests is required when:

- a participant meets one of the conditions outlined Algorithm A or Algorithm B or
- in the presence of abnormal liver chemistry not meeting protocol-specified stopping rules, if the investigator believes that it is in the best interest of the participant.

[figure not shown]
Algorithm A: Phase 3 Liver Chemistry Stopping Criteria and Increased Monitoring Algorithm

Abbreviations: ALT = alanine transaminase; INR = international normalized ratio; SAE = serious adverse event; ULN = upper limit of normal

Refer to Section 10.6 for required Liver Safety Actions and Follow up Assessments.

Algorithm B : Phase 3 Liver Chemistry Increased Monitoring Algorithm with Continued Study Intervention for Participants with ALT ≥ 3 xULN but <8 xULN

Abbreviations: ALT = alanine transaminase; INR = international normalized ratio; SAE = serious adverse event; ULN = upper limit of normal, Tbili = Total bilirubin.

Refer to Section 10.6 for required Liver Safety Actions and Follow up Assessments.

7.1.2. QTc Stopping Criteria

Adult Participant

- If a clinically significant finding is identified (including, but not limited to changes from baseline in QT interval corrected using Bazett's formula [QTcB] or Fridericia's formula [QTcF]) after enrollment, the investigator or qualified designee will determine if the participant can continue in the study and if any change in participant management is needed. This review of the ECG printed at the time of collection must be documented. Any new clinically relevant finding should be reported as an AE.
- A participant who meets the bulleted criteria based on the average of triplicate ECG readings will be withdrawn from study intervention:
 - QTc > 500 msec OR Uncorrected QT > 600 msec
 - Change from baseline of QTc > 60 msec

For patients with underlying bundle branch block, follow the discontinuation criteria listed below:

Baseline QTc with Bundle Branch Block	Discontinuation QTc with Bundle Branch Block
< 450 msec	> 500 msec
450 – 480 msec	≥ 530 msec

- The same QT correction formula must be used for each individual participant to determine eligibility for and discontinuation from the study. This formula may not be changed or substituted once the participant has been enrolled. (Note: Ideally, all ECGs for a participant should be performed with the same ECG machine.)
 - For example, if a participant is eligible for the protocol based on QTcB, then QTcB must be used for discontinuation of this individual participant as well.
 - Once the QT correction formula has been chosen for a participant's eligibility, the same formula must continue to be used for that participant for all QTc data being collected for data analysis. Other nonprotocol-specified ECGs are an exception.
- The QTc should be based on the average of triplicate ECG readings obtained over a brief (e.g., 5- to 10-minute) recording period.

Participant ≥ 12 to < 18 years of age

For any participant ≥ 12 to < 18 years of age, if the participant has an abnormal ECG reading during the study treatment, the investigator or qualified designee will determine if the participant can continue in the study and if any change in participant management is needed.

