2.3.1. Risk Assessment

Potential Risk of Clinical Significance	Summary of Data/Rationale for Risk	Mitigation Strategy
Gepotidacin (GSK2140944)		

Cardiovascular Effects Based on nonclinical data, cardiovascular effects were reversible increase in heart rate and blood pressure (dog and monkey); reversible 10 to 21 msec (4% to 9%) increase in QTc (monkey); and at the highest dose, a reversible 2 to 3 msec (6% to 8%) increase in QRS (monkey). Based on a thorough QTc clinical study, gepotidacin may cause mild, reversible heart rate effects and QT prolongation.
	
In a thorough QTc study, infusion of gepotidacin at doses of 1000 and 1800 mg over 2 hours caused a mild increased heart rate effect of approximately 6 to 10 bpm and QT prolongation measured as $\Delta\Delta QTcF$ of 12 to 22 msec. The QT prolongation evolved during the infusion and was quickly reversed over 2 hours after the end of the infusion (see the IB for details). In Phase I studies, concentration-dependent QT prolongation has been observed during clinical trials with gepotidacin; however, this increase has not translated into clinically significant QTc values or changes from baseline (change from baseline >60 msec or QTcF >500 msec) or cardiovascular AEs. In Phase I and II studies, gepotidacin did not have a clinically relevant effect on cardiac conduction (PR and QRS intervals). Although there appears to be a trend to higher gepotidacin systemic exposure in healthy Japanese compared to Western subjects, the higher systemic exposure of gepotidacin observed in Japanese subjects is currently considered to be within the tolerable range and not associated with any cardiovascular safety concerns.
	
See Section 5.2 for excluded cardiac conditions. Close monitoring of clinical parameters and AEs (Section 1.3) will be conducted, and treatment monitoring and evaluation criteria (Section 7.1.2) will be utilized to mitigate cardiovascular effects. Participants taking medications known to increase QT or potent CYP3A4 inhibitors will be excluded (see Section 6.8.2). See also the Renal and Hepatic sections within this table below.

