20. The participant is taking QT-prolonging drugs or drugs known to increase the risk of torsades de pointes (TdP) per the www.crediblemeds.org. “Known Risk of TdP” category at the time of her Baseline Visit, which cannot be safely discontinued from the Baseline Visit to the TOC Visit; or the participant is taking a strong cytochrome P450 enzyme 3A4 (CYP3A4) inhibitor.
21. For any participant ≥ 12 to <18 years of age, the participant has an abnormal ECG reading at Baseline.
22. The participant has a QTc >450 msec or a QTc >480 msec for participants with bundle branch block.

Note:

- The QTc is the QT interval corrected for heart rate according to either Bazett’s formula (QTcB), or Fridericia’s (QTcF) formula, and/or another method. It is either machine read or manually overread.
- The specific formula used to determine eligibility and discontinuation for an individual participant should be determined prior to initiation of the study. In other words, several different formulas cannot be used to calculate the QTc for an individual participant and then the lowest QTc value used to include or discontinue the participant from the trial.

23. The participant has a documented or recent history of uncorrected hypokalemia within the past 3 months.
24. The participant has a known alanine aminotransferase (ALT) value $>2 \times$ upper limit of normal (ULN).
25. The participant has a known total bilirubin value $>1.5 \times$ ULN (isolated bilirubin $>1.5 \times$ ULN is acceptable if bilirubin is fractionated and direct bilirubin $<35\%$).
26. The participant has cirrhosis or current unstable liver or biliary disease per investigator assessment defined by the presence of ascites, encephalopathy, coagulopathy, hypoalbuminemia, esophageal or gastric varices, or persistent jaundice.

Note: Stable noncirrhotic chronic liver disease (including Gilbert's syndrome, asymptomatic gallstones, and chronic stable hepatitis B or C [e.g., presence of hepatitis B surface antigen or positive hepatitis C antibody test result]) is acceptable if the participant otherwise meets entry criteria.

27. The participant has a previous history of cholestatic jaundice/hepatic dysfunction associated with nitrofurantoin.

Prior/Concomitant Therapy

28. The participant has received treatment with other systemic antimicrobials or systemic antifungals within 1 week before study entry.

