#### **4.6.3.3. ECG**

The number of participants with worst case QTc values relative to potential clinical importance criteria which are post-baseline relative to baseline will be summarised. The summary will include baseline data and worst case post-baseline, and visits (i.e. On-Therapy and TOC visits). The baseline categories are: Low, within Range and High for PCI criteria. The change categories for PCI criteria are: To Low, To within Range or No Change, To High. The determination of worst case post-baseline takes into account both planned and unscheduled assessments. A summary of change from baseline in ECG values will be produced by visit.

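### The QT correction formula may differ between participants while the SAP summarises one unlabelled QTc, so mean changes and counts above 450 msec can mix Bazett and Fridericia values

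*Protocol*

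**What the plan says.** **Protocol.** Section 5.2 introduces the term with "The QTc is the QT interval corrected for heart rate according to either Bazett" and goes on to admit Fridericia's "formula, and/or another method". It asks for the formula to be settled before the study starts, but at the level of the person: "several different formulas cannot be used to calculate the QTc for an individual participant". Section 7.1.2 repeats the within-participant rule and gives a Bazett case as its example: "if a participant is eligible for the protocol based on QTcB, then QTcB must be used for discontinuation of this individual participant as well". It then extends the rule beyond eligibility and discontinuation: "the same formula must continue to be used for that participant for all QTc data being collected for data analysis". No study-wide formula is set.

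**SAP.** Section 4.6.3.3 plans two ECG summaries. One is categorical ("The number of participants with worst case QTc values relative to potential clinical importance criteria"); the other is change from baseline by visit. Section 6.2.3.1 supplies one QTc row with an upper limit of 450 msec. Neither section names a formula, re-derives QTc or splits by formula.

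**Drug background.** Protocol 2.3.1 reports that, in a thorough QTc study, infusion of gepotidacin "caused a mild increased heart rate effect of approximately 6 to 10 bpm", with a placebo-corrected QTcF effect of 12 to 22 msec.

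**The concern.** The two corrections respond differently to heart rate. Above 60 bpm Bazett gives a larger value than Fridericia, and the gap widens as the rate rises. A drug that raises heart rate therefore produces a larger change from baseline in a participant followed on QTcB than in one followed on QTcF, even if QTcF itself does not move.

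QT prolongation is a named risk of gepotidacin. Mean change from baseline in ECGs is a summary measure of the secondary safety estimand (Protocol Section 3, Table 1). The Day 1 postdose and On-therapy ECGs are timed near the expected maximum concentration (Protocol 1.3), when a concentration-related rate effect would be easiest to see. If formulas are mixed, the mean change and the counts above 450 msec depend partly on which formula was chosen for whom, and the tables would not reveal it.

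**Working it through.** The documents give no figure for the difference between the formulas, so there is none to reproduce. Its size follows from the definitions.

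**Inputs from the documents**
- Heart-rate rise d: 6 to 10 bpm (Protocol 2.3.1; infusions of 1000 and 1800 mg over 2 hours).
- Category limit: above 450 msec (SAP 6.2.3.1).

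**Assumptions, not in the documents**
- Baseline heart rate 65 to 75 bpm and QTcF 400 to 420 msec; central case 70 bpm and 400 msec; wider range 60 to 90 bpm and 380 to 420 msec.
- Share s of participants on Bazett: unknown, 0% to 100%; the rest on Fridericia.

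**Formula.** With RR = 60/HR in seconds, QTcB = QT/RR^(1/2) and QTcF = QT/RR^(1/3). Hence QTcB = QTcF × (HR/60)^(1/6).

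**Step 1: excess in one Bazett participant, QTcF held constant.** Excess = QTcF × [((HR + d)/60)^(1/6) − (HR/60)^(1/6)].
- Central case at baseline: 400 × (70/60)^(1/6) = 410.4 msec.
- After +6 bpm: 400 × (76/60)^(1/6) = 416.1 msec, an excess of 5.7 msec.
- After +10 bpm: 400 × (80/60)^(1/6) = 419.6 msec, an excess of 9.2 msec.
- Over 65 to 75 bpm and 400 to 420 msec: 5.4 msec (75 bpm, 400 msec, +6) to 10.3 msec (65 bpm, 420 msec, +10).
- Over the wider range: 4.4 to 10.9 msec.

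**Step 2: with a true effect.** In the central case, a QTcF rise of 12 msec at +6 bpm reads as 412 × (76/60)^(1/6) − 410.4 = 18.1 msec on Bazett. A rise of 22 msec at +10 bpm reads as 422 × (80/60)^(1/6) − 410.4 = 32.3 msec.

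**Step 3: effect on the arm mean.** Excess in the mean = s × excess per Bazett participant (central case).

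| Bazett share | +6 bpm | +10 bpm |
|---|---|---|
| 0% | 0 | 0 |
| 25% | 1.4 msec | 2.3 msec |
| 50% | 2.8 msec | 4.6 msec |
| 75% | 4.2 msec | 6.9 msec |
| 100% | 5.7 msec | 9.2 msec |

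**Step 4: effect on the difference between arms.** The formula is chosen before treatment, so s is equal in the two arms on average. The excess in the difference is then s × (excess on gepotidacin − excess on nitrofurantoin). It vanishes if heart rate changes equally in both arms, and equals the table above if only gepotidacin raises it.

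**Step 5: meaning of the 450 msec limit.** A QTcB of 450 corresponds to a QTcF of 450/(70/60)^(1/6) = 438.6 msec at 70 bpm and 450/(80/60)^(1/6) = 428.9 msec at 80 bpm. This needs no drug effect on heart rate. At 65 to 75 bpm and QTcF of 400 to 420 msec, QTcB already exceeds QTcF by 5.4 to 15.9 msec.

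**The case against.** **Pooling is inferred.** The SAP never says that values from different formulas are combined. It does not list its ECG parameters in full, and programmers could tabulate QTcB and QTcF separately. That is correct. But the protocol directs one chosen formula per participant into the analysis data, and the SAP offers one QTc variable and one limit. Mixing is what results if both texts are followed as written.

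**Bazett may be rare or absent.** Also correct: no document gives the share, and with none there is no effect. Section 7.1.2 does foresee such a participant, so the plan cannot assume zero.

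**The heart-rate figure is from infusion.** This stands. The regimen here is 1500 mg orally twice daily, no heart-rate effect is given for it, and Protocol 4.3 predicts a QTcF effect in Japanese participants below that seen in earlier studies with clinically relevant QTc changes. The excess may be smaller than computed. The offset at the 450 msec limit does not depend on it.

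**One formula per participant is consistent, and randomisation balances the choice.** Both help. The first keeps each participant's change on one scale; the second removes the fixed offset from the comparison of arms on average. Neither removes Bazett's dependence on rate, nor gives the overall counts a single meaning.

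**Comparison with the thorough QTc study.** A reader might infer that using QTcF throughout would make the results directly comparable with the 12 to 22 msec cited. It would not: that figure is placebo-corrected and from infusion, and this trial has no placebo-only arm. Comparability is not the ground for the change.

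**Conclusion.** The protocol permits formulas to differ between participants in the data for analysis, and the SAP does nothing to separate or harmonise them. That follows from the text. The size is conditional: about 5 to 10 msec per Bazett participant under the assumed baseline values and the infusion-based rate rise, scaled in the arm mean by an unknown share. In the central case this is 1.4 to 2.3 msec at 25% and nothing at 0%. The difference between arms is affected only so far as the heart-rate rise differs by arm. The count above 450 msec has no single meaning under a mixture, since at 70 to 80 bpm a QTcB of 450 is a QTcF of about 429 to 439.

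A reader might go further and conclude that the trial will report a spurious QT signal of 5 to 10 msec, or that participant-level decisions are unsound. The documents support neither. The first needs everyone on Bazett and the full infusion effect. The second is not in question, because each participant's eligibility and discontinuation are judged on one formula throughout.

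This should be fixed. It does not threaten the trial's conclusion: the ECG summaries are descriptive secondary safety results, and the primary consistency analysis is untouched.

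**What to change.** 1. In SAP 4.6.3.3 and 6.2.3.1, name QTcF as the variable for mean change and for categories, derived for every participant from the QT and heart rate of each ECG. Show QTcB separately, as supportive.
2. First confirm that both inputs are in the database for each ECG. Protocol 8.2.3 says the machine calculates heart rate and measures QT; it does not say that both are captured for every replicate.
3. In Protocol 7.1.2, confine the sentence on keeping one formula to eligibility and discontinuation, so that it no longer governs the analysis data. Leave those clinical rules and their limits unchanged.
4. Record the change in SAP 4.9, because deriving QTcF for all departs from the present 7.1.2 wording.

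The cost is a few lines of SAP text, one derived variable, one extra supportive table and a wording change in the protocol. If QT or heart rate proves not to have been captured, data retrieval is an added cost. With one formula for everyone, the between-formula excess is zero by construction.

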Nitrofurantoin has been selected as the active reference in this study. Nitrofurantoin is globally available as the indication for the treatment of acute uncomplicated UTI (acute cystitis) caused by susceptible strains of *E. coli* or *S. saprophyticus* in most regions except for Japan and is a recommended oral first-line treatment for acute uncomplicated cystitis per current US and European Association of Urology guidelines [Gupta, 2011b; EAU, 2019]. Although nitrofurantoin is not approved in Japan, nitrofurantoin was a marketed antimicrobial in Japan until 1990 and showed efficacy in Japanese patients with acute uncomplicated cystitis and had no clinically significant safety issues [Tsunoda, 1970; Ookita, 1970; Tofukuji, 1970]. Both gepotidacin and nitrofurantoin will be administered BID for a treatment duration of 5 days. As described in Section 4.3, the dose of each study treatment and the 5-day duration were selected to provide efficacious treatment for acute uncomplicated cystitis. Having the same dose regimen will also support double-blind dose administration.

Both adult and adolescent (≥ 12 to <18 years of age) eligible female participants will be enrolled in this double-blinded study. The study is restricted to female participants since this study is conducted as bridging-like study to assess the consistency between this study and the global studies, which was planned per FDA guidance [DHHS, 2019]. Adolescent participants will only be enrolled at study sites where investigators have experience in this population and if allowed per the study site's institutional ethics committees and enrollment will be contingent upon such approvals. Adolescent assent forms and adult consent forms will be developed with oversight from local governing institutional review boards (IRBs)/independent ethics committees (IECs) (see 10.1). There is no upper age limit for study participants; however, participants are excluded if they reside in a nursing home or dependent care type-facility, or if they have any comorbidities associated with complicated UTI. Thus, any participants >75 years of age will only be eligible for the study if they are residing independently.

In order to maximize the efficiency of this study while minimizing discomfort and inconvenience to participants consenting to this protocol, a GSK SRT will monitor

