8. STUDY ASSESSMENTS AND PROCEDURES

- Study procedures and their timing are summarized in the SoA (Section [1.3](#)).
- Protocol waivers or exemptions are not allowed
- Immediate safety concerns should be discussed with the sponsor immediately upon occurrence or awareness to determine if the participant should continue or discontinue study intervention.
- Adherence to the study design requirements, including those specified in the SoA, is essential and required for study conduct.
- All screening evaluations must be completed and reviewed to confirm that potential participants meet all eligibility criteria. The investigator will maintain a screening log to record details of all participants screened and to confirm eligibility or record reasons for screening failure, as applicable.
- Procedures conducted as part of the participant's routine clinical management (e.g., blood count) and obtained before signing of ICF may be utilized for screening or baseline purposes provided the procedure met the protocol-specified criteria and was performed within the timeframe defined in the SoA.
- Prescreening activities may be conducted, including a prescreening informed consent and urine testing, as further detailed in the SRM. The required baseline urine

specimen may be collected as part of an optional prescreening process, if not already part of standard of care, and is further detailed in the SRM. This specimen can be used for the required baseline procedures of the diagnosis of presumptive acute uncomplicated cystitis and pregnancy testing.

- Laboratory results that could unblind the study will not be reported to investigative sites or other blinded personnel until the study has been unblinded.
- The maximum amount of blood collected from each participant over the duration of the study, including any extra assessments that may be required, will not exceed 200 mL.
- Repeat or unscheduled samples may be taken for safety reasons or for technical issues with the samples.
- Participants may return to the study site at any time due to AEs or if they are experiencing new or continuing signs and symptoms of acute cystitis. Participants will be assessed and treated per the investigator's judgement. If a participant is switched to a different antimicrobial before or during the TOC Visit, all TOC procedures should be completed before the other antimicrobial is started.

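### Section 7.1.2 sets mandatory numeric QTc stops for adults but none for participants aged 12 to <18

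*Protocol*

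**What the plan says.** Section 7.1.2 of the protocol has two age headings.

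Under the adult heading there are two layers. First, the investigator reviews any clinically significant ECG finding and decides whether the participant can go on. Second, there is a hard rule: "A participant who meets the bulleted criteria based on the average of triplicate ECG readings will be withdrawn from study intervention". The criteria are "QTc > 500 msec OR Uncorrected QT > 600 msec" and "Change from baseline of QTc > 60 msec". Adults with bundle branch block have their own table: stop above 500 msec if baseline QTc is below 450 msec, and at 530 msec or more if baseline is 450 to 480 msec.

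Under the heading for ages 12 to <18 there is one sentence. It says that "if the participant has an abnormal ECG reading during the study treatment, the investigator or qualified designee will determine if the participant can continue", and that the same person decides on any change in management. It contains no QTc, QT or change-from-baseline value.

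The protocol does set ECG limits for adolescents at entry. Exclusion 21 removes anyone aged 12 to <18 if "the participant has an abnormal ECG reading at Baseline". Exclusion 22 has no age split: "The participant has a QTc >450 msec or a QTc >480 msec for participants with bundle branch block".

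**The concern.** Gepotidacin has a recognised, concentration-dependent QT effect (Section 2.3.1). Adolescents receive the adult dose, and dose modification is not allowed (Section 6.5). After a single 1500 mg dose their Cmax was 27% higher than in adults, although the range and AUC were similar (Section 4.3).

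Against that background, adults have investigator judgement backed by a mandatory ceiling, and minors have judgement with no ceiling. The younger group is therefore held to a weaker stopping rule on a known risk. The liver and renal stopping criteria (Sections 7.1.1 and 7.1.3) make no such age distinction, and the protocol does not explain why QTc does.

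What is at stake is participant safety and consistent conduct across sites. The primary estimand and its analysis are not in question.

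**Working it through.** This is mainly a comparison of text. The plan states no figure to reproduce. The arithmetic below only gauges how often the gap could matter and how much exposure would remain if it did.

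**1. Is there a numeric on-treatment stop for minors anywhere else?**

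| Place | What it provides for ages 12 to <18 | Mandatory stop at a value? |
|---|---|---|
| Protocol 5.2, exclusions 21 and 22 | Normal baseline ECG; QTc not above 450 msec (480 with bundle branch block) | No, entry only |
| Protocol 7.1 | Investigator may stop treatment at any time | No, discretionary |
| Protocol 7.1.2, adolescent paragraph | Review of any abnormal ECG | No |
| Protocol 8 | Sponsor discussion of immediate safety concerns | No |
| Protocol 8.2.3 | Triplicate ECGs; refers back to 7.1.2 for withdrawal criteria | No |
| Protocol 1.3 | ECG timing; refers back to 5.2, 7.1.2 and 8.2.3 | No |
| SAP 4.6.3.3 and 6.2.3.1 | QTc above 450 msec as a category of potential clinical importance | No, summary only |

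The count of mandatory numeric stops for this group is zero.

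**2. Same reading, two ages.** Take a triplicate-average QTc of 505 msec on treatment.
- Adult without bundle branch block: 505 > 500, so withdrawal is required.
- Age 17: the reading is abnormal, so the investigator reviews it and may allow dosing to continue. If it is treated as an immediate safety concern, the sponsor is consulted as well.

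**3. How likely is a breach?** The inputs are the 450 msec entry ceiling (exclusion 22, no bundle branch block) and the largest mean placebo-corrected QTcF effect in the thorough QT study, 22 msec after intravenous dosing (Section 2.3.1).
- Absolute limit: 450 + 22 = 472 msec, and 500 − 472 = 28 msec short of the limit.
- Change limit: 60 − 22 = 38 msec short of the limit.

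The 22 msec is a group mean from intravenous dosing, and individual values vary around it. The sums show that breaches should be uncommon; they are not a safety margin for any one participant.

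Other evidence points the same way. Phase I increases did not exceed 500 msec or a 60 msec change (Section 2.3.1). Predicted prolongation in Japanese participants lies below earlier values of concern, and the adolescent risk profile was similar to that of adults (both Section 4.3).

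**4. How much dosing would remain after a breach?** The course is 10 doses (Section 6.8.2). I assume two doses per 24-hour treatment day, counted from the first dose.
- After the Day 1 post-dose ECG: 10 − 1 = 9 doses.
- After the On-therapy ECG: Day 2 starts with dose 3 and Day 4 ends with dose 8, so between 10 − 3 = 7 and 10 − 8 = 2 doses.

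**The case against.** The strongest reply is that the split is deliberate and in some ways stricter for minors. They need a normal ECG to enter. Any abnormal on-treatment reading triggers review, whereas the adult text asks for a clinically significant one. A QTc above 500 msec would be abnormal, so review is certain and only its outcome is open. Section 4.2 adds that "Adolescent participants will only be enrolled at study sites where investigators have experience in this population", and Section 8 says "Immediate safety concerns should be discussed with the sponsor immediately upon occurrence or awareness to determine if the participant should continue or discontinue". Adverse event reporting and the blinded Safety Review Team sit behind these. Keeping a teenager on drug at 505 msec would take an experienced investigator choosing to continue despite all of this.

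These safeguards are real and lower the risk. None of them requires stopping at any value, and the baseline exclusion acts only before dosing. If investigators would always stop in such a case, a written limit costs nothing; the same argument would make the adult limit unnecessary, yet the protocol keeps it.

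A second reply is that the numeric criteria were meant for everyone. Section 8.2.3, the risk table in 2.3.1 and the note to exclusion 22 all refer to QTc withdrawal or discontinuation without an age limit. That sits awkwardly with having no criterion for minors and may reflect the intention. But the criteria stand under the adult heading and adolescents have a separate one, so a site would naturally read them as adult-only. If universal coverage was intended, the same edit is needed as a clarification.

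The point that few participants would be affected stands in full. It limits the weight of the concern without removing it.

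**Conclusion.** The concern holds. As written, the three mandatory QTc limits apply to adults only, and participants aged 12 to <18 have no mandatory numeric stop in either document.

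The practical size is small. Breaches should be rare, and because the documents plan no number of adolescents, the number affected may be near zero. If a breach did occur, most of the course could still be ahead. The conclusion rests on reading the age headings in Section 7.1.2 at face value; the dose counts rest on two doses per treatment day. This is a change to consider on safety grounds, with no bearing on the validity of the primary result.

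**What to change.** In Section 7.1.2, move the three existing limits (triplicate-average QTc above 500 msec, uncorrected QT above 600 msec, QTc rise above 60 msec) out from under the adult heading and state them as mandatory withdrawal criteria at every age. Keep investigator review of any abnormal ECG as an additional step for ages 12 to <18.

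Nothing else in the section needs extending. The single-formula rule (note to exclusion 22) and the triplicate requirement (Section 8.2.3) already cover all ages, and exclusion 21 leaves essentially no adolescents to whom the bundle-branch-block table could apply.

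The cost is a short protocol amendment with IRB/IEC approval and perhaps a rare extra adolescent discontinuation of treatment. Triplicate ECGs are already scheduled, so no procedure is added. Treatment discontinuation is already handled by the treatment policy strategy, so the primary analysis method does not change.
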